12.2. Appendix 2: Assessment Windows

Clinic visits are scheduled to take place as specified in the protocol. Unscheduled visit will be excluded from analyses on any population. For all clinic visits, nominal visit days and times will be used for reporting; for example, if a subject recorded value on the Week 4 visit that were made on Week 3 of treatment, they will be presented as Week 4 values.

If a subject withdraws at a scheduled visit, and these data were scheduled to be collected at that visit, the data will be summarised and analysed (as appropriate) together with data from subjects who did not withdraw. If a subject withdraws at a scheduled visit at which these data were not scheduled to be collected, or if a subject withdraws between scheduled visits, data will be slotted to the next visit where the data was scheduled to be collected according to the study flowchart. The protocol visits windows of ± 3 days should be applied to the assignment of withdrawal visits, so that if a subject withdraws within the appropriate number of days from the last visit where that data was scheduled to be collected, they would get that data slotted to that visit and otherwise the data will be slotted to the next scheduled visit.

The early withdrawal visit will then be re-labelled as the corresponding visit. The same approach will be followed to Post Treatment 1 and Post Treatment 2 visits.

If there is more than one assessment associated with a particular visit interval, then the latest assessment will be used for summary tables and analyses. Where two or more findings (e.g. ECG (i.e. site interpretations will be used), laboratory data) slot to the same visit interval, the most 'abnormal' results will be used, i.e. according to the following hierarchy: Abnormal-Clinically Significant > Abnormal – not clinically significant > Normal.

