8.4.1. ECG

All sites used a standardised ECG equipment provided by a centralised external vendor. A central ECG reader was used. The site and vendor provided ECG interpretation, while the site differentiates between “Abnormal – Not Clinically Significant and Abnormal – Clinically significant”, the vendor only specifies ‘Abnormal’. There are differences between the site vs vendor interpretations (i.e. the site interpretation = abnormal vs vendor = normal and site = normal vs vendor = abnormal).

As site interpretations also take into consideration assessment from investigators of patients, the site interpretations will be used for summaries (i.e. even though for patients, vendor = abnormal vs site = normal) but both the site and vendor interpretations will be listed.

Actual and change from baseline QTcF category values will be summarized for each visit. Actual QTcF value is categorized as: ≤ 450 , >450 to ≤ 480 , >480 to ≤ 500 , and >500 . Change from baseline QTcF value is categorized as: ≤ 30 , >30 to ≤ 60 and >60 . In addition, listing will be produced for subject meeting the criteria of actual QTcF >500 msec or change from baseline >60 msec.

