12.4.2. Reporting Standards

General

 The current GSK Integrated Data Standards Library (IDSL) will be applied for reporting, unless otherwise stated (IDSL Standards Location: https://spope.gsk.com/sites/IDSLLibrary/SitePages/Home.aspx): 
 4.03 to 4.23: General Principles 5.01 to 5.08: Principles Related to Data Listings 6.01 to 6.11: Principles Related to Summary Tables 7.01 to 7.13: Principles Related to Graphics
Formats

 GSK IDSL Statistical Principles (5.03 & 6.06.3) for decimal places (DP's) will be adopted for reporting of data based on the raw data collected, unless otherwise stated. Numeric data will be reported at the precision collected on the eCRF. The reported precision from non eCRF sources will follow the IDSL statistical principles but may be adjusted to a clinically interpretable number of DP's.
Planned and Actual Time

 Reporting for tables, figures and formal statistical analyses: 
 Planned time relative to dosing will be used in figures, summaries, statistical analyses and calculation of any derived parameters, unless otherwise stated. The impact of any major deviation from the planned assessment times and/or scheduled visit days on the analyses and interpretation of the results will be assessed as appropriate. Reporting for Data Listings: 
 Planned and actual time relative to study drug dosing will be shown in listings (Refer to IDSL Statistical Principle 5.05.1). Unscheduled or unplanned readings will be presented within the subject's listings.

Unscheduled Visits	

 • Unscheduled visits will not be included in summary tables and/or figures. • All unscheduled visits will be included in listings. 	
Descriptive Summary Statistics	
Continuous Data	Refer to IDSL Statistical Principle 6.06.1
Categorical Data	N, n, frequency, %
Graphical Displays	

 • Refer to IDSL Statistical Principals 7.01 to 7.13. 	

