12.5. Appendix 5: Derived and Transformed Data

12.5.1. General

Multiple Measurements at One Analysis Time Point

 If there are two values within a time window (as per Section 12.2.1) then the latest assessment will be used. Participants having both High and Low values for Normal Ranges at any post-baseline visit for safety parameters will be counted in both the High and Low categories of “Any visit post-baseline” row of related summary tables. This will also be applicable to relevant Potential Clinical Importance summary tables.
Study Day

 Calculated as the number of days from Randomization Date: 
 Ref Date = Missing → Study Day = Missing Ref Date < Randomization Date → Study Day = Ref Date – Randomization Date Ref Date ≥ Randomization Date → Study Day = (Ref Date – Randomization Date) + 1

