3.28.	Safety	LB3	Summary of Chemistry Shifts from Baseline Relative to Normal Range		SAC
3.29.	Safety	LB3	Summary of Emergent Chemistry Results (Relative to the Potential Clinical Concern Range)	ICH E3	SAC

Safety: Tables					
No.	Population	IDSL / Example Shell	Title	Programming Notes	Deliverable
Laboratory: Haematology					
3.30.	Safety	LB1	Summary of Haematology Changes from Baseline	ICH E3 Includes Baseline values.	SAC
3.31.	Safety	LB3	Summary of Haematology Shifts from Baseline Relative to Normal Range		SAC
3.32.	Safety	LB17	Summary of Emergent Haematology Results (Relative to the Potential Clinical Concern Range)	ICH E3	SAC
ECG					
3.33.	Safety	EG1	Summary of ECG Findings	The ECG findings to be summarized are the ECG interpretation, clinical significance of abnormal ECGs	SAC
3.34.	Safety	EG2	Summary of Change from Baseline in ECG Values by Visit	Includes Baseline values.	SAC
3.35.	Safety	EG10	Summary of Actual and Change from Baseline QTc(F) Values by Category	Category column will be replaced and created based on the information provided in the Section 8.4.1. For Anytime Post-Baseline, the highest post-baseline QTcF value and the change from baseline for this highest post-baseline QTc value is categorised	SAC
Vital Signs					
3.36.	Safety	VS1	Summary of Change from Baseline in Vital Signs	Includes Baseline values.	SAC
3.37.	Safety	VS3	Summary of Worst Case Vital Signs Results by PCI Criteria Post-Baseline Relative to Baseline		SAC

Safety: Tables					
No.	Population	IDSL / Example Shell	Title	Programming Notes	Deliverable
Immunogenicity					
3.38.	Safety	SAF_T3	Summary of Binding Antibody by Visit		SAC
3.39.	Safety	SAF_T4	Summary of Neutralising Antibody by Visit		SAC
3.40.	Safety	SAF_T5	Summary of Binding Antibody Assay Results: Highest Treatment Emergent Confirmatory Result Any Time Post Baseline		SAC

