12.9.12. ICH Listings

ICH: Listings					
No.	Population	IDSL / Example Shell	Title	Programming Notes	Deliverable
Subject Disposition					
1.	Screened	ES7	Listing of Reasons for Screen Failure	Journal Guidelines	SAC
2.	ITT	ES2	Listing of Reasons for Study Withdrawal	ICH E3	SAC
3.	ITT	SD2	Listing of Reasons for Study Treatment Discontinuation	ICH E3	SAC
4.	ITT	BL1	Listing of Participants for Whom the Treatment Blind was Broken	ICH E3	SAC
5.	ITT	TA1	Listing of Planned and Actual Treatments	IDSL	SAC
Protocol Deviations					
6.	ITT	DV2	Listing of Important Protocol Deviations	ICH E3	SAC
7.	ITT	IE3	Listing of Participants with Inclusion/Exclusion Criteria Deviations	ICH E3	SAC
Demographic and Baseline Characteristics					
8.	ITT	DM2	Listing of Demographic and Baseline Characteristics	ICH E3 Include Baseline Eosinophil Count and Fitzpatrick skin type	SAC
9.	ITT	DM9	Listing of Race	ICH E3	SAC
Prior and Concomitant Medications					
10.	ITT	CM3	Listing of Concomitant Medications	ICH E3	SAC
Exposure					
11.	Safety	EX3	Listing of Exposure Data	ICH E3	SAC

CONFIDENTIAL

205050

ICH: Listings					
No.	Population	IDSL / Example Shell	Title	Programming Notes	Deliverable
Adverse Events					
12.	Safety	AE8	Listing of All Adverse Events	ICH E3	SAC
13.	Safety	AE7	Listing of Participant Numbers for Individual Adverse Events	ICH E3	SAC
14.	Safety	AE2	Listing of Relationship Between Adverse Event System Organ Classes, Preferred Terms, and Verbatim Text	IDSL	SAC
15.	Safety	AE8	Listing of Adverse Events Leading to Withdrawal from Study / Permanent Discontinuation of Study Treatment		SAC
16.	Safety	AE8	Listing of Adverse Events Reported on the Day of Dosing		SAC
17.	Safety	AE8	Listing of All Adverse Events of Special Interest	Produced only if more than one AESI reported.	
All Laboratory					
18.	Safety	LB5	Listing of All Chemistry Laboratory Data for Participants with Any Value of Potential Clinical Importance	ICH E3	SAC
19.	Safety	LB5	Listing of All Haematology Laboratory Data for Participants with Any Value of Potential Clinical Importance	ICH E3	SAC
20.	Safety	LB14	Listing of Laboratory Data with Character Results		SAC
21.	Safety	LIVER5	Listing of Liver Monitoring/Stopping Event Reporting		
22.	Safety	LIVER13	Listing of Subjects Meeting Hepatobiliary Laboratory Criteria Post-Baseline		
ECG					
23.	Safety	EG3	Listing of ECG Values (Participants with QTcF >500 msec or Increase > 60 msec from Baseline)		SAC
24.	Safety	EG5	Listing of Abnormal ECG Findings	IDSL	SAC

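### The SAP drops unscheduled visits from every table and figure, with no exception for worst-case, any-time or maximum safety displays, so these can miss the extreme they are labelled to show (minor)

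*SAP*

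**What the plan says.** Two sections of the SAP set the rule. Section 12.2 (Appendix 2, Assessment Windows) says: "Unscheduled visit will be excluded from analyses on any population". Section 12.4.2 (Reporting Standards) says: "Unscheduled visits will not be included in summary tables and/or figures". It then adds: "All unscheduled visits will be included in listings".

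The SAP also plans safety displays that are defined by an extreme value after baseline:

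- **Table 3.37:** "Summary of Worst Case Vital Signs Results by PCI Criteria Post-Baseline Relative to Baseline".
- **Table 3.35, any-time row:** the programming note begins "For Anytime Post-Baseline, the highest post-baseline QTcF value". Section 8.4.1 sets the top categories at above 500 msec for the actual value and above 60 msec for the change from baseline.
- **Figures 3.1 and 3.2:** maximum ALT against baseline ALT, and maximum ALT against maximum total bilirubin.
- **Any-visit laboratory rows:** section 12.5.1 describes an any-visit post-baseline row for normal-range tables and adds: "This will also be applicable to relevant Potential Clinical Importance summary tables". It does not number the tables.

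Two listings select subjects on the same kind of criterion. Listing 25 covers vital signs for participants with any value of potential clinical importance. For QTcF, section 8.4.1 says a "listing will be produced for subject meeting the criteria of actual QTcF >500 msec or change from baseline >60 msec"; this is Listing 23.

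**The concern.** Leaving unscheduled visits out of by-visit rows is ordinary practice. A row labelled worst case, highest or maximum makes a different promise: a reader takes it to cover everything measured after baseline. Under the written rule it covers scheduled visits and slotted withdrawal visits only. Extra visits tend to happen because something is wrong, so the rule removes the measurements most likely to hold an extreme. The table and its companion listing can then disagree on the same threshold, and someone who reads only the table would not know that a more extreme value exists.

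**Working it through.** The plan gives no figure to reproduce here. The check sets the rules against the displays.

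**1. Is there an exception anywhere?** I looked in SAP 8.2 to 8.4, 12.2, 12.4, 12.5.1, 12.6 and the display list in 12.9. Two rules come close, and neither readmits unscheduled visits.
- The most-abnormal rule in 12.2 applies to findings slotted to the same visit interval. It ranks normal and abnormal interpretations, not numeric values.
- The any-visit rule in 12.5.1 only says that a subject with both high and low values is counted in both categories.

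**2. Vital signs (Table 3.37 against Listing 25).** Protocol 4.2.4 creates an unscheduled visit for suspected flare and has its assessments completed once flare is confirmed. Protocol Table 4 includes vital signs among them without the only-if-needed condition it puts on physical examination and chemistry. SAP 12.7.2 flags systolic pressure below 85 or above 160 mmHg. Take a subject with a systolic pressure above 160 at a flare visit and every scheduled reading between 85 and 160:
- Listing 25 includes the subject, because listings keep unscheduled visits.
- Table 3.37 shows no high systolic value for the subject, because the visit is excluded.

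**3. QTcF (Table 3.35 against Listing 23).** Protocol 5.4.5 and Table 3 allow clinically indicated unscheduled ECGs. After baseline, ECGs are planned only at Week 4, Week 16 and Early Withdrawal. An illustration with assumed values, not taken from the documents:

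| ECG | QTcF (msec) | Change from baseline (msec) |
|---|---|---|
| Baseline | 430 | – |
| Week 4 | 440 | 440 − 430 = 10 |
| Extra visit | 505 | 505 − 430 = 75 |
| Later planned ECG | 445 | 445 − 430 = 15 |

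- As written, the any-time row uses max(440, 445) = 445, so the subject falls in the categories up to 450 and up to 30.
- Listing 23 includes the subject, since 505 > 500 and 75 > 60.
- With the extra visit admitted, the row uses 505 and 75, and table and listing agree.

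Slotting the Early Withdrawal ECG under 12.2 does not repair this when it is a later measurement: it contributes its own value, not the earlier extreme. If the extreme is recorded at the Early Withdrawal visit itself, it does reach the table.

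**4. How far does the ECG case reach?** Both exclusion sentences speak of visits. The flare visit is the only visit type the protocol names as unscheduled, and its schedule contains no ECG. Weeks 8, 12 and 20 are scheduled visits without a planned ECG, so an ECG added there is not plainly excluded. SAP 12.4.2 mentions unscheduled or unplanned readings separately, but only to place them in listings. The ECG mismatch is therefore clear for extra visits and unsettled for unplanned ECGs at scheduled visits.

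**5. Liver and other laboratory displays.** Protocol Appendix 8 calls for weekly repeat chemistries during liver monitoring, which fall between the four-weekly visits, so the maxima in Figures 3.1 and 3.2 are affected in principle. The programming note to Figure 3.1 indicates that no liver events were reported, and chemistry at a flare visit is done only if needed, so the effect may be nil. Hematology is required at flare visits, so a hematology table with an any-visit row could be affected. Which tables carry that row is my inference (probably 3.28, 3.29, 3.31 and 3.32).

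**The case against.** The strongest reply is that SAP 12.4.2 states both halves of the rule side by side. A table and a listing that differ under a disclosed rule do not contradict each other, and keeping symptom-driven measurements out of comparisons between arms is defensible. That stands for by-visit rows and for the eosinophil model, which section 10.1.4.1 already limits to scheduled visits. It does not justify calling a value highest or worst when a known higher or worse one was left out.

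A second reply is that the programming note for Table 3.35 is specific to that row and could be read as overriding the general rule. A programmer might read it so, but the note says nothing about unscheduled data, and Table 3.37 has no note at all.

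A third is that these displays use shells from the sponsor's standards library, which Appendix 10 does not reproduce. Section 12.4.2 applies that library only where the SAP does not state otherwise, and here the SAP states its own rule. The missing shells do limit what can be said about the laboratory tables.

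A fourth is that such a subject would be seen elsewhere. The QTcF cut-offs are protocol stopping criteria, so the case should appear among the reasons for withdrawal or discontinuation (Tables 1.1 and 1.2, Listings 2 and 3), and a clinically significant abnormality is an adverse event. This softens the ECG case. It helps less for vital signs, where a value in the concern range is not itself a stopping criterion.

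A reader might go further and infer that every unscheduled ECG is lost from Table 3.35. The wording about visits does not support that. Nor does the interval between the Week 4 and Week 16 ECGs measure the loss: it describes the protocol's schedule and contains two scheduled visits at which an added ECG may well count.

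**Conclusion.** The point holds and is minor. Followed as written, SAP 12.2 and 12.4.2 can make Table 3.37 and the any-time row of Table 3.35 show a value that is not the worst or highest, and can make them disagree with Listings 25 and 23. Figures 3.1 and 3.2 are affected in principle. Laboratory tables are affected only if their shells carry an any-visit row.

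The realised effect is unknown. The documents give no count of unscheduled values and do not show that any crossed a cut-off. A reader might convert one omitted subject into a percentage of an arm, but that presupposes an event nobody has shown and a final arm size the documents do not give. Nor should a reader infer hidden safety data or a disturbed efficacy result: listings keep all unscheduled visits, the displays concerned are descriptive, and no efficacy analysis depends on this point.

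The conclusion assumes that the general exclusion is applied literally to the named displays.

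**What to change.** Amend SAP 12.2 and 12.4.2 to read, in substance: *Unscheduled visits and readings are excluded from by-visit rows and models only. Any-time, maximum and worst-case post-baseline safety displays use all post-baseline values, scheduled or unscheduled, and take the most extreme value.* Naming readings as well as visits settles the question of ECGs added at Weeks 8, 12 and 20. The closing clause is needed because 12.2 and 12.5.1 otherwise take the latest of several values in an interval.

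Apply this to Table 3.37, the Anytime Post-Baseline row of Table 3.35, Figures 3.1 and 3.2, and any laboratory table confirmed from its shell to have an any-visit row. Footnote these displays to say that unscheduled measurements are symptom-driven and that their number differs between subjects.

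The cost is a sentence or two in each section, a changed data filter for two tables and two figures (plus any confirmed laboratory tables), and the footnote. No new data are needed, and by-visit rows and the eosinophil model do not change. The one drawback is that maxima based on unequal numbers of measurements compare less cleanly between arms, which the footnote discloses. A footnote alone, with the exclusion left in place, would explain the mismatch but would still leave rows that do not show what their labels say.

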7.5. Pharmacokinetics

7.5.1. Blood Sample Collection

Blood samples for determination of mepolizumab plasma concentration will be collected at the time points indicated in [Table 3](#). The PK samples will be drawn **pre-dose** on days when study treatment is scheduled to be administered. The actual date and time of each blood sample collection will be recorded. The timing of PK samples may be altered and/or PK samples may be obtained at additional time points to ensure thorough PK monitoring.

Blood samples (approximately 2 mL) for determination of plasma concentrations of mepolizumab will be collected into plastic lithium heparin tubes.

Processing, storage and shipping procedures are provided in the laboratory manual.

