9.1.1.1. Drug Concentration Measures

Mepolizumab plasma concentrations will be summarised and listed by nominal time. Standard summary statistics will be calculated.

Refer to [Appendix 5: Data Display Standards & Handling Conventions](#) (Section [12.5.3 Reporting Standards for Pharmacokinetic](#)).

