10.1.2. Summary Measure

- Geometric Means for ratio to baseline in blood eosinophil counts and for absolute blood eosinophil count at each visit.
- Only listings will be presented for biomarker endpoints.

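### The SAP's visit-slotting rule has no exemption for PK, so early stoppers' 8-week post-dose samples and samples taken days after a dose are averaged as 4-week troughs

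*SAP*

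**What the plan says.** SAP 9.1.1.1: "Mepolizumab plasma concentrations will be summarised and listed by nominal time". SAP 12.2 sets the general convention: "For all clinic visits, nominal visit days and times will be used for reporting". For a withdrawal between visits, "data will be slotted to the next visit where the data was scheduled to be collected according to the study flowchart". A short look-back comes first: "The protocol visits windows of ± 3 days should be applied to the assignment of withdrawal visits", so data within 3 days after a scheduled visit go back to that visit. The withdrawal visit is then relabelled, and "The same approach will be followed to Post Treatment 1 and Post Treatment 2 visits". If two assessments share a slot, "then the latest assessment will be used for summary tables and analyses".

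SAP 12.6.1 applies this slotting to withdrawal visits without limiting it to efficacy. The schedule in SAP Appendix 1 collects PK and haematology at Early Withdrawal and at Week 20 (Post-Treatment Visit 2). Protocol 5.4.1 places the two post-treatment visits 4 and 8 weeks after the last dose, whenever that was. Protocol 7.5.1 has PK drawn before dosing on dosing days, and adds: "The actual date and time of each blood sample collection will be recorded".

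For eosinophils, SAP 10.1.2 asks for "Geometric Means for ratio to baseline in blood eosinophil counts and for absolute blood eosinophil count at each visit".

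**The concern.** For a subject on schedule, the Week 4, 8, 12 and 16 samples are all taken 4 weeks after a dose. The slotting rule puts samples with a different dosing history under the same labels, and nothing in SAP 9.1 or 12.4.3 takes them out.

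Derived PK parameters were dropped after termination (SAP 9.1.1.2), so Table 4.1 and Figures 4.1 and 4.2 are all the summarised PK output there is. The amendment log in Protocol Appendix 15 says that the Week 8 and 12 samples were added to describe steady state in atopic dermatitis. After a stop for futility, a reader will also look to these displays, and to the eosinophil summary in Table 5.1, to judge whether exposure and depletion were adequate. Rows that mix dosing histories make the visit means harder to interpret and widen the SD.

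**Working it through.** **1. Planned drop-out.** Protocol 4.3 gives 50 evaluable, 10% drop-out and 56 randomised. 50 / 0.9 = 55.6, rounded up to 56, so the figure reproduces. Per arm this is 28, and 10% is about 3 subjects.

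**2. Where the rule puts each sample.** PK is scheduled at Weeks 4, 8, 12, 16 and 20, with no Baseline sample.

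| Last dose | Post-Treatment 1 (4 wk) | Post-Treatment 2 (8 wk) | Early Withdrawal, day 1-3 | Early Withdrawal, day 4 on |
|---|---|---|---|---|
| Baseline | Week 4 | **Week 8** | **Week 4** | **Week 4** |
| Week 4 | Week 8 | **Week 12** | **Week 4, replaces trough** | **Week 8** |
| Week 8 | Week 12 | **Week 16** | **Week 8, replaces trough** | **Week 12** |
| Week 12 | Week 16 | Week 20 | **Week 12, replaces trough** | **Week 16** |

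Bold cells carry the wrong time since dose, except that an Early Withdrawal sample close to 4 weeks after the dose is nearly right. Post-Treatment Visit 1 is always placed correctly. If it is attended, it supersedes an Early Withdrawal sample slotted forward to the same visit.

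**3. Size of a washout sample.** The documents give no half-life or time to peak. Assumption, for scale only: one compartment, half-life 14 to 28 days, peak at 4 to 8 days. Once absorption is complete, the fraction remaining after 28 days is r = 2^(-28/half-life), which is 0.25 at 14 days and 0.50 at 28 days. The ratio of the slotted 8-week sample to the true value in its row is then:

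- Week 8 (one dose against two): r / (1 + r) = 0.25/1.25 = 0.20, to 0.50/1.50 = 0.33
- Week 12 (two against three): (r + r²) / (1 + r + r²) = 0.3125/1.3125 = 0.24, to 0.75/1.75 = 0.43
- Week 16 (three against four): (r + r² + r³) / (1 + r + r² + r³) = 0.328/1.328 = 0.25, to 0.875/1.875 = 0.47

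**4. Size of an early post-dose sample.** Each dose given at time d contributes ka/(ka - ke) × [exp(-ke(t - d)) - exp(-ka(t - d))] at time t. Here ke = ln 2 / half-life, and ka solves ln(ka/ke)/(ka - ke) = time to peak. The ratio C(28 + k)/C(28), with doses at days 0 and 28, is:

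| Half-life, peak | k = 1 day | k = 3 days |
|---|---|---|
| 14 d, 4 d | 2.81 | 3.85 |
| 14 d, 8 d | 1.66 | 2.45 |
| 28 d, 4 d | 2.14 | 2.66 |
| 28 d, 8 d | 1.53 | 2.10 |

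So the sample is about 1.5 to 3.9 times the Week 4 trough. After later doses the trough is higher and the ratio smaller. For a subject who exits without Post-Treatment Visit 1, a sample 10 days after the Week 4 dose, labelled Week 8, is 1.5 to 2.4 times the true value.

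**5. Effect on a row mean.** If a share f of a row's records has ratio q, the mean changes by f(q - 1). With f = 0.10 in the Week 12 row: 0.10 × (0.24 - 1) = -7.6%, to 0.10 × (0.43 - 1) = -5.7%. This takes all the planned drop-outs as stopping after the Week 4 dose and attending Post-Treatment Visit 2. The effect is proportional to f.

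**The case against.** **Does slotting apply to PK at all?** SAP 12.5.3 invokes it by name for IGA and EASI; the PK sections do not. SAP 12.4.3 refers PK displays to company standards that are not in the documents, and SAP 12.4.2 calls for planned time relative to dosing in summaries unless otherwise stated. This is a fair point about intent. But SAP 12.2 and 12.6.1 are general, and no text exempts PK. For an early stopper's Post-Treatment Visit 2, planned time relative to dosing is 8 weeks, which conflicts with the slotted label. The text needs settling either way.

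**How often?** A reader might infer that washout samples must be common because the sponsor terminated the study. The documents do not support that. Protocol 5.4.2 lists termination among the reasons for leaving the study, and Protocol 4.2.2 has such subjects complete one Early Withdrawal visit and exit, so they would have no 8-week sample. Protocol 5.4.1 also lists termination under treatment discontinuation, so which path applied is not settled. The only planned rate is 10%. The overwrite in the 1-to-3-day window also needs a decision to stop within days of a dosing visit.

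**Can a reader still see what happened?** Largely, with effort. Figures 4.1 and 4.2 plot individual concentrations, and listings show actual time relative to dosing (SAP 12.4.2). It would go too far to say that adequacy of exposure could not be judged. The visit means and SDs would still be mixed.

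**Eosinophils.** Trough and peak are concentration terms and do not carry over. The MMRM's use of all scheduled-visit measurements in SAP 10.1.4.1 is an estimand choice, not an error. What stands is that early stoppers' 8-week counts are relabelled as on-treatment visits. No size can be given for this.

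**Conclusion.** The concern holds as a defect in a stated rule. Followed literally, SAP 12.2 mislabels three kinds of PK sample: early stoppers' 8-week samples, Early Withdrawal samples 1 to 3 days after a dose, and mid-interval samples from subjects who leave without Post-Treatment Visit 1. The direction follows from the text and from any declining concentration after the peak. The sizes (0.20 to 0.47, 1.5 to 3.9, and a 6 to 8% fall at 10%) rest on the assumed half-life and time to peak. The last also assumes that all drop-outs land in one row, and it would grow if early stops were commoner.

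The reach is limited. PK and eosinophils are exploratory and PK is descriptive only. A reader might take the point as casting doubt on the primary result; it does not, because that result rests on IGA response with its own non-responder rule. The change is worth making because these tables are the study's remaining summary of exposure and depletion.

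**What to change.** - **SAP 9.1.1.1 and 12.2:** state that PK is exempt from slotting and from replacement by the latest assessment.
- **Table 4.1 and Figure 4.2:** keep in each visit row only samples taken at that scheduled visit on the protocol's own schedule: pre-dose, or Post-Treatment Visit 1 for the matching number of doses. Completers' Week 20 samples stay where they are. Do not add a 28 ± 3 day filter. With ±3 days on each visit, a compliant interval runs from 28 - 6 = 22 to 28 + 6 = 34 days. A dose postponed 2 weeks under Protocol 5.4.3, with the next on the original schedule, gives about 14.
- **Off-schedule samples:** show Early Withdrawal samples and early stoppers' Post-Treatment Visit 2 samples separately, by time since last dose and number of doses. One pooled 8-week row would mix again: under the same assumptions, 8 weeks after one dose is 1/(1 + r + r² + r³) = 0.53 to 0.75 of a completer's Week 20 value.
- **Table 5.1:** do not relabel early stoppers' 8-week eosinophil counts as on-treatment visits; show them separately. For the MMRM, state explicitly whether off-treatment values are included; the choice is the sponsor's.

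The cost is SAP wording and minor programming from dose and sample dates already recorded, and a somewhat smaller n at some visits.
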